## 1.6 Integration of multifaceted data by artificial intelligence

All these new echocardiography-based measures have significantly improved our understanding of the nature of LBBB, its cardio-mechanic effect and the hemodynamic consequences of abnormal electrical activation. Thus, these new measures alone have high potential to improve the selection of adequate treatment strategy. Furthermore, it had been shown that the presence of LBBB morphology on ECG is not always associated with typical mechanical patterns. 30% of patients with LBBB on ECG selected for CRT did not have typical contraction patterns as indicated by speckle tracking strain echocardiography (40). The mismatch between ECG and myocardial mechanics was independently associated with increased risk of adverse outcome. Conversely typical dyssynchrony patterns were observed in 20-26% of patients without typical LBBB morphology at ECG, where the majority responded to CRT (26). All these findings clearly demonstrate that echocardiography may have high potential for accurately selecting patients needing CRT independently of ECG morphology.

As a result of computer-models (38), experimental and clinical studies (36), the interplay of delayed electrical activation, afterload, global and regional myocardial function and the influence on ventricular dyssynchrony or inefficient myocardial work is much better understood. In addition to ECG criteria and

assessment of ejection fraction (EF), echocardiography renders useful information about ventricular loading and function. However, to date CRT management is only based on EF, QRS length, LBBB morphology and NYHA class with a failure rate of still >30% (41). Several echocardiographic studies on CRT response have shown that the failure rate would be expected to be dramatically reduced if imaging would be involved (40,41,45,46).

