## **2 Hypotheses, aims and objectives:**

### **2.1 Primary hypotheses**

1. Typical strain-pattern and myocardial work assessment improve substantially prediction of heart failure development, hospital admission, death and adverse cardiovascular events and can help to establish more effective patient selection criteria for CRT or medical heart failure treatment.
2. AI, incorporating strain imaging and myocardial work assessment as well as conventional clinical patient characteristics is able to improve additionally risk assessment and treatment response in the LBBB population

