### 3.10 Statistical power

It is unknown how high the percentage in this study population will be who suffer from deterioration of LV function. Therefore, a pilot-study on the first 100 study-subject of the different subgroups will be performed in order to calculate the power of the final population size. Pilot participants will be included into the final study population. Assuming different proportions of 5%, 10%, 20% and 30% of patients with deteriorating ventricular function, a difference in septal or global strain between at 5% at a SD of  $\pm 6\%$  the sample size needed for hypothesis 1 in each subgroup will be 220, 129, 73 or 57, respectively for a two-sided test and a Type I error of 0.05.

For calculation of hazard-ratios between patients with against without deterioration of LV function for the primary outcome variable: hospital admission due to CVD, assumed that 5% of all patients either

deteriorate function and the presence of decreased segmental work indicates at least a relative risk of 1.8, at an alpha of 0.05 with 500 patients included, the statistical power will be 82%.

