### 3.11 Statistics

Patients with deteriorating myocardial function will be identified by increasing proBNP by more than 10%, increasing NYHA class, increasing diastolic volume by more than 10% and/or decreasing EF by more than 5%. ANOVA will be used to compare parameters between patients with deteriorating myocardial function and those with unchanged clinical condition after one year. ROC curve analysis will serve to find the ideal cut-off values for continuous variables and assessing sensitivity and specificity of the tests. Univariate and multivariate logistic regression tests will be performed in order to identify the most powerful parameters predicting development of heart-failure with hospital admissions as primary outcome and predicting death (or transplantation) as secondary outcome.

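### Hypothesis 1 claims better prediction, but neither power calculation is sized for added value and no planned analysis is set against the conventional markers

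*Protocol*

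**What the plan says.** - **Protocol 2.1, primary hypothesis 1:** "Typical strain-pattern and myocardial work assessment improve substantially prediction of heart failure development, hospital admission, death and adverse cardiovascular events". The same sentence expects this to give better selection criteria for CRT or medical treatment.
- **Protocol 1.6** describes present practice, to which an improvement would naturally be compared: "CRT management is only based on EF, QRS length, LBBB morphology and NYHA class".
- **Protocol 3.10, first calculation:** "Assuming different proportions of 5%, 10%, 20% and 30% of patients with deteriorating ventricular function", with "a difference in septal or global strain between at 5% at a SD of" 6%, two-sided alpha 0.05. The size "in each subgroup will be 220, 129, 73 or 57, respectively". It is tied to hypothesis 1 by name ("the sample size needed for hypothesis 1 in each subgroup"). No power is stated for it.
- **Protocol 3.10, second calculation:** a relative risk of at least 1.8 for reduced segmental work, 500 patients, 82% power. No adjustment is mentioned.
- **Protocol 3.11:** "ANOVA will be used to compare parameters" between deteriorated and unchanged patients. ROC curves serve to choose cut-offs and report sensitivity and specificity. Univariate and multivariate logistic regression serve to pick out the strongest predictors of heart failure with hospital admission, and of death or transplantation.

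**The concern.** To say that a marker improves prediction is to say that it adds something to what is already known about the patient. A difference in mean strain between patients who deteriorate and those who do not shows only that strain is associated with deterioration. If EF carries the same information, strain can differ clearly between the groups and still add nothing.

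The protocol itself says which calculation serves hypothesis 1, and that calculation answers the question of association. The analyses in 3.11 do not close the gap, because none is designated as the test of added value. At stake is the study's main claim. A significant strain difference, or an ROC curve with no reference curve beside it, could be presented as grounds for selecting patients for an invasive therapy, without evidence that selection would be better than with EF, QRS, morphology and NYHA.

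**Working it through.** **1. Reproducing the stated sizes.** Inputs from 3.10: difference 5, SD 6, so d = 5/6 = 0.833; two-sided alpha 0.05; total N split p : (1 - p). Power comes from the two-sample t-test with noncentrality d x sqrt(n1 n2/(n1 + n2)).

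| Share deteriorating | Stated N | Power at stated N |
|---|---|---|
| 5% | 220 | 76% |
| 10% | 129 | 80% |
| 20% | 73 | 80% |
| 30% | 57 | 81% |

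Three of the four match an unadjusted t-test at 80% power, which is an inferred value. The 5% figure is short: 80% needs 238 (normal approximation) or 240 (t). That is a side observation. What matters here is that the sizing contains no allowance for EF or any other marker.

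**2. What the planned effect means for prediction.** For normal markers with equal SD, AUC = Phi(d/sqrt 2) = Phi(0.833/1.414) = 0.72. The protocol gives no AUC for the conventional markers to set beside it.

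**3. How often a redundant marker would be significant.** Suppose strain correlates rho with EF and is unrelated to outcome once EF is known. If EF differs by D SD between the groups, strain differs by rho x D SD. The protocol gives neither rho nor D, so both are assumptions and a range is shown. At 5% deteriorating, N = 220 gives 11 v 209 with noncentrality (rho x D) x sqrt(11 x 209/220) = 3.23 x rho x D. N = 1000 gives 50 v 950, with 6.89 x rho x D.

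| rho | D (SD) | Strain difference (SD) | Significant, 11 v 209 | Significant, 50 v 950 |
|---|---|---|---|---|
| 0.5 | 0.5 | 0.25 | 13% | 41% |
| 0.5 | 0.8 | 0.40 | 25% | 79% |
| 0.7 | 0.5 | 0.35 | 20% | 67% |
| 0.7 | 0.8 | 0.56 | 44% | 97% |
| 0.7 | 1.0 | 0.70 | 62% | >99% |
| 0.7 | 1.2 | 0.84 | 77% | about 100% |

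Every row has zero added value by construction.

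**4. What a test of added value does with the same marker.** Simulation at the four stated sizes, with (rho, D) = (0.7, 0.8), (0.7, 1.19) and (0.8, 1.04): the mean-strain test is significant in 44-82% of studies. The likelihood-ratio test of strain added to EF rejects in 5-7%, close to its nominal level.

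**5. What adjustment costs.** For the same standardised effect after adjustment for EF, N rises by roughly 1/(1 - rho^2).

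| rho | 5% | 10% | 20% | 30% |
|---|---|---|---|---|
| none (stated) | 220 | 129 | 73 | 57 |
| 0.5 | 294 | 172 | 98 | 76 |
| 0.7 | 432 | 253 | 144 | 112 |
| 0.8 | 612 | 359 | 203 | 159 |

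**The case against.** **Hypothesis 1 is not tied to ANOVA.** A reader might infer that it is to be tested only as a difference in mean strain. The protocol does not say so: 3.11 also lists ROC analysis and multivariate logistic regression, and assigns none of them to hypothesis 1. A regression holding both EF and strain could show independent value. This stands, and the point is limited accordingly. But the regression is described as a search for strong predictors, no calculation sizes it for added value, and its outcomes are admission and death, whereas the first calculation splits patients by deterioration.

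**Covariates and performance measures belong in an SAP.** Correct, and their absence here is not the complaint. The complaint is what the protocol fixes: a named calculation for hypothesis 1 that measures something else. A later SAP could add a nested model, but the stated sizes would still not have been derived for it.

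**The high pass rates need favourable inputs.** A reader might infer that a redundant marker would pass. Only could is supported. An EF difference of 1.0-1.2 SD means that EF alone has an AUC of Phi(1.0/1.414) = 0.76 to Phi(1.2/1.414) = 0.80. At rho 0.7 the upper end gives a strain difference of 0.84 SD, essentially the planned 0.833, so near-planned power follows by construction. With weaker inputs the rate at 11 v 209 falls to 13%. At 50 v 950 it stays at 41% or more over the range shown.

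**The comparator is partly a reviewer's choice.** Section 1.6 lists what guides CRT decisions, not an established model for predicting deterioration. That is fair, but improvement needs some comparator, and this is the one the protocol criticises.

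**Conclusion.** The point holds as a mismatch between claim and sizing. Neither calculation in 3.10 is sized for added value, and 3.11 fixes no comparison with the conventional markers, so the plan as written could declare hypothesis 1 met without answering it. This follows from the text and does not depend on the assumed inputs.

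The size of the risk does depend on them: about 13% to 77% at 11 v 209 and about 41% to 100% at 50 v 950, for strain-EF correlations of 0.5-0.7 and EF differences of 0.5-1.2 SD, neither of which the protocol gives. The documents do not support saying that a redundant marker is bound to pass, or that a mean comparison is the only planned test. The matter should be corrected; it does not invalidate the design.

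**What to change.** **Section 3.11.** Make the test of hypothesis 1 a nested logistic comparison in the pooled cohort of about 1000 patients, and name its outcome.
- Base model: a small prespecified set, namely EF, QRS duration, NYHA class, and LBBB versus paced type.
- Extended model: the base plus one prespecified strain measure and one prespecified work measure.
- Report a likelihood-ratio test and the optimism-corrected change in AUC with its confidence interval. Use penalisation if events are few.
- Keep ANOVA and ROC cut-offs as descriptive.

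The comparison should not be run within each subgroup. With at least six coefficients, 11 events give fewer than two per coefficient (11/6 = 1.8). Pooled at 5% there would be 50 events (50/6 = 8.3), which is still modest and is why the marker set must stay small.

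**Section 3.10.** State that 220, 129, 73 and 57, and the 82% figure, apply to unadjusted association only. Use the planned pilot to state the precision expected for the added-value test.

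**Cost.** No new data: ECG, echocardiography and clinical assessment are already planned. The text changes are short, but this is a real re-sizing. The adjusted test has less power than the unadjusted one (220 becomes about 432 at correlation 0.7), so the stated sizes will look less favourable.

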## 3 Project arrangements, method selection and analyses

### 3.1 Patients

This is a longitudinal prospective cohort-study intending to include at least 1000 patients with LBBB from University Hospital of North Norway Tromsø and Harstad, Akershus University Hospital, Lørenskog, Oslo University Hospital, Rikshospitalet, Haukeland University Hospital, Bergen and Nordlands Hospital, Bodø, over a 2-year inclusion period.

Information about present and previous diseases, medication, surgical- or invasive treatment, PM, ICD or CRT implantation, clinical examination and present and previous echocardiographic imaging and blood samples (Hb, Thrombocytes, CRP, Kreatinine, eGFR, Urate, HbA1C, Cholesterol, ProBNP, Troponins, ALAT and Ferritin) will be accessed by the patient's journal.

All prospective study participants will answer one customized and two standardized (EQ5D and HeartQoL) questionnaires. They will undergo general clinical investigation comprising height and weight measurements, baseline ECG, blood samples when not found in the patient's journal, standardized BP measurements and echocardiography with a 3 minutes- hand-grip test at baseline and in a 18 month follow-up study.

Clinical outcome data including death and hospital admissions due to heart failure and CRT implantation will be assessed after 3 and 5 years (eventually after 10 and 15 years) by linkage to data from the patient's clinical records through access to Norwegian Patient Registry (Norsk pasientregister (NPR)), Norwegian Causes of Death Registry (Dødsårsaksregisteret) and Norwegian Cardiovascular Disease Registry (Hjerte- og karregisteret).

St Olavs Hospital, Trondheim, might provide retrospective patient data with echocardiography loops, where outcome-data will be extracted from the same registries.

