### 3.4 Primary outcome

Deterioration, stability or improvement of markers for myocardial function over time. Outcome-variables will be measured by deterioration or non-deterioration of LV function by defining deterioration of ventricular function by using either echocardiographic parameters that are classically used for the definition of CRT responders: EF decrease by >5% with EF initially <55% or >10% with EF initially  $\geq$  55%, LV diastolic or systolic volume enlargement by 10%, NYHA class deterioration or proBNP increase by >10%.

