### 3.5 Secondary outcomes

Hospital admissions, adverse cardiovascular events, mortality, CRT implantation and initiation of medical treatment for heart failure.

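### Protocol 3.10: the 82% power for hospital admission holds for the comparison it names only if about 80-90% or more of the 500 patients are admitted, which the protocol does not state

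*Protocol*

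**What the plan says.** Section 3.10 introduces the calculation as "For calculation of hazard-ratios between patients with against without deterioration of LV function for the primary outcome variable: hospital admission due to CVD". It assumes that 5% of all patients deteriorate, and continues that to "deteriorate function and the presence of decreased segmental work indicates at least a relative risk of 1.8". The full statement of effect, error rate, size and result is "at least a relative risk of 1.8, at an alpha of 0.05 with 500 patients included, the statistical power will be 82" per cent.

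No section gives a proportion admitted or an event count. Section 3.1 plans registry follow-up, "Clinical outcome data including death and hospital admissions due to heart failure and CRT implantation will be assessed after 3 and 5 years", but 3.10 does not use either time point. The planned cohort is also larger than the 500 in the calculation: "intending to include at least 1000 patients with LBBB".

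On the role of admission, 3.10 calls it primary, and so does 3.11 for the logistic regression. Section 3.4 instead defines the primary outcome as "Deterioration, stability or improvement of markers for myocardial function over time", and 3.5 lists as secondary "Hospital admissions, adverse cardiovascular events, mortality, CRT implantation and initiation of medical treatment for heart failure".

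The same section sizes the strain comparison for 5%, 10%, 20% and 30% deteriorating: "the sample size needed for hypothesis 1 in each subgroup will be 220, 129, 73 or 57, respectively for a two-sided test". No target power is given for these sizes.

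**The concern.** Power for a hazard ratio depends on the number of events, and the sentence supplies patients instead. It also defines the groups by LV deterioration and then ties the effect to decreased segmental work, whose prevalence is not given. It uses two effect measures, hazard ratio and relative risk.

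This is the only power stated for hospital admission, an outcome that two sections call primary. If the figure rests on almost every patient being admitted, a reader cannot judge from it whether a null result for admission would be informative.

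**Working it through.** **Inputs from 3.10:** N = 500; 5% deteriorating, so 25 versus 475; effect 1.8, ln 1.8 = 0.5878; alpha 0.05. I take alpha as two-sided, which 3.10 states only for the strain sizes. Admission proportions are my assumptions throughout.

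**1. Reproducing the 82%.** Schoenfeld: power = Φ(√(D·p·(1−p))·ln 1.8 − 1.96), with p = 0.05, so p(1−p) = 0.0475.

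- D = 500: √23.75 = 4.873; 4.873 × 0.5878 − 1.96 = 0.905; power 81.7%.
- D = 400: 72.6%. D = 250: 52.6%. D = 150: 34.8%.
- Events for 82%: (1.960 + 0.915)² / (0.5878² × 0.0475) = 504.

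The printed figure is therefore recovered by entering the number of patients as the number of events.

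**2. Checking the approximation.** With only 5% exposed, Schoenfeld is somewhat pessimistic. I simulated the log-rank test (exponential times, common censoring, 25 versus 475, hazard ratio 1.8; 20,000 runs per row):

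| Admitted | Power, N = 500 |
|---|---|
| 30% | 49% |
| 50% | 66% |
| 80% | 80% |
| 90% | 83% |
| 100% | 84% |

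So 82% needs roughly 80-90% of patients admitted, not literally all of them.

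**3. Other routes to 82%.**

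- *Decreased segmental work as the exposure.* Events needed = 23.93 / (p(1−p)), where 23.93 = 2.875² / 0.5878². At 10, 20, 30 and 50% exposed this is 266, 150, 114 and 96 events, or 53% down to 19% of 500 patients admitted. Neither the prevalence nor the admission proportion is stated.
- *Two proportions, 25 versus 475, risk ratio 1.8.* About 35.5% versus 63.9% admitted gives 82%. Neither proportion appears in the protocol.
- *One-sided test.* Schoenfeld gives (1.645 + 0.915)² / (0.5878² × 0.0475) = 400 events, which is 80% admitted. Neither a one-sided test nor that proportion is stated.
- *Odds ratio of 1.8 per SD of a continuous predictor, 5% having the outcome.* Φ(√(500 × 0.05 × 0.95) × 0.5878 − 1.96) = 81.7%. This fits the logistic regression in 3.11, but contradicts the hazard-ratio wording and the present/absent factor in 3.10.

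**4. The planned size.** The same simulation with 50 versus 950:

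| Admitted | Power, N = 1000 |
|---|---|
| 20% | 60% |
| 30% | 75% |
| 40% | 84% |
| 50% | 90% |

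**5. Strain sizes (minor).** Noncentral t, two-sided 0.05, d = 5/6: 129 (13 v 116) gives 80.7%, 73 (15 v 58) gives 81.0%, and 57 (17 v 40) gives 80.7%. The size for the 5% case, 220 (11 v 209), gives 76.5%; 240 (12 v 228) gives 80.0%.

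**The case against.** The best defence is that nothing has been miscalculated: the four printed inputs put straight into a standard formula give 81.7%. That is correct. A reader might infer that 82% cannot be reproduced at all, and the calculation shows otherwise. If segmental work is the exposure, moderate admission proportions are enough. What remains is that every route needs something the protocol does not say or goes against what it does say.

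A statistical analysis plan might supply the admission rate and method. That would excuse an omitted detail, but here the protocol prints a specific power for a described comparison.

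The figure is also provisional. Sections 3.7 and 3.10 say a pilot of 100 will inform the final size, and at least 1000 patients are planned. This limits the practical consequence, and a reader should not conclude that the study is underpowered for admission. However, the pilot is to assess heart failure incidence and ventricular deterioration; CVD admission, the missing input, is not listed.

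Two further inferences are not supported. Section 3.1 mentions heart-failure admissions where 3.10 uses CVD admissions, but its list is introduced as inclusive rather than complete, so the two are compatible. And 220 is not shown to be wrong: it falls short only of an 80% target that the protocol never states.

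**Conclusion.** The point stands as a badly fixed power statement, not as an arithmetic slip. For the hazard-ratio comparison that 3.10 describes, 82% with 500 patients requires about 80-90% or more to be admitted for CVD; at 30-50% admitted, power is about 49-66%. At 1000 patients it runs from about 60% to 90% as the proportion admitted goes from 20% to 50%. These figures rest on a two-sided test, 5% exposed, a constant hazard ratio of 1.8 and my assumed admission proportions. They are not bounds, because other readings of the sentence give other values.

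Two contradictions need no calculation: the effect is assigned to a different factor from the one that defines the groups, and admission is primary in 3.10 and 3.11 but secondary in 3.5. This should be fixed; the uneven strain sizes are minor.

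**What to change.** Replace the 82% sentence in 3.10 with one that states:

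- a single exposure (LV deterioration or decreased segmental work) and its assumed prevalence;
- a single effect measure for the 1.8;
- the assumed proportion with a CVD admission and the horizon;
- the sidedness and method;
- the power for the planned size of at least 1000.

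If the hazard-ratio comparison with 5% deteriorating is meant, it could read: *With 1000 patients, 5% with LV deterioration and a hazard ratio of 1.8, two-sided log-rank power at 0.05 is about 75% if 30% are admitted for CVD within the stated horizon and 84% if 40% are.* The sponsor should put in its own admission proportion. The 5% should not be carried over to segmental work unless that is intended.

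Add CVD admission to what the pilot in 3.7 records. Reconcile 3.4 and 3.5 with 3.10 and 3.11 on whether admission is primary or secondary. For strain, state the target power; if it is 80%, give 240 for the 5% case, or state that 220 gives 76.5%.

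The cost is rewording, one pilot item and one outcome label. The rewording itself needs no extra patients or visits, but the stated power may become less favourable.

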### 3.11 Statistics

Patients with deteriorating myocardial function will be identified by increasing proBNP by more than 10%, increasing NYHA class, increasing diastolic volume by more than 10% and/or decreasing EF by more than 5%. ANOVA will be used to compare parameters between patients with deteriorating myocardial function and those with unchanged clinical condition after one year. ROC curve analysis will serve to find the ideal cut-off values for continuous variables and assessing sensitivity and specificity of the tests. Univariate and multivariate logistic regression tests will be performed in order to identify the most powerful parameters predicting development of heart-failure with hospital admissions as primary outcome and predicting death (or transplantation) as secondary outcome.

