This study will include prospectively clinical patients from the cardiological outpatients' clinics, and the cardiology wards in University Hospital of North Norway Tromsø and Harstad, Akershus University Hospital, Lørenskog, Oslo University Hospital, Rikshospitalet, Haukeland University Hospital, Bergen and Nordlands Hospital, Bodø. Furthermore, we intend to use retrospectively collected data of population-based study from the Katholieke Universiteit (KU) Leuven, Belgium and invite participants with LBBB or predominant ventricular pacing (PVP) from the Tromsø 7 study for the prospective study. The study is furthermore open to include retrospectively datasets where subjects with LBBB or PVP can be identified and echocardiographies are taken (e.g. St. Olav Hospital, Trondheim). Prospectively included patients will be followed by a repeated echocardiography study after one year and access to patient registries through 5 years (eventually up to 15 years). All studies abroad will follow their own study protocol and follow-up.

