### 3.7 Exclusion criteria

Typical RBBB. No ability to give informed consent, non-cardiovascular co-morbidities with reduced life-expectancy < 1 year or patients with complex congenital heart disease.

In-hospital patients will be included during the in-hospital period and the baseline echocardiogram and BP monitoring will be performed as part of the routine clinical investigations. From the “Out-patients’ clinics the patients will be recruited after assessing ECGs from patient’s records.

In a Pilot-study feasibility of patient recruitment will be tested. The incidence of heart failure and deterioration of ventricular function in the first 100 included patients will be assessed in order to define the power of the final study-population size.

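### The marker-based primary classification ignores heart-failure events and treatment between the two visits, so a patient who worsens and fully recovers counts as non-deteriorated

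*Protocol*

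**What the plan says.** Section 3.4 of the protocol gives the primary outcome as "Deterioration, stability or improvement of markers for myocardial function over time" and then makes it binary: "Outcome-variables will be measured by deterioration or non-deterioration of LV function". The criteria are thresholds of change in ejection fraction, left ventricular volume, NYHA class and proBNP. Section 3.11 repeats the rule with slightly different components: "Patients with deteriorating myocardial function will be identified by increasing proBNP by more than 10%, increasing NYHA class", together with diastolic volume and ejection fraction, joined by and/or. The comparison built on this rule follows in the same section: "ANOVA will be used to compare parameters between patients with deteriorating myocardial function and those with unchanged clinical condition after one year".

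There is one repeat examination. The Background says "Prospectively included patients will be followed by a repeated echocardiography study after one year"; section 3.1 puts the follow-up at 18 months.

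Events between the visits appear elsewhere. Section 3.5 lists, as secondary outcomes, hospital admissions and "initiation of medical treatment for heart failure". Section 3.11 takes hospital admissions as the primary outcome of the logistic regression. Section 2.3 puts heart failure development and admissions among the primary objectives. Neither 3.4 nor 3.11 says how an admission, or treatment started between the visits, enters the marker-based classification.

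**The concern.** All four kinds of criterion are ones that heart-failure treatment can move back towards baseline. A two-point comparison cannot tell a patient who stayed stable from one who worsened, was treated and recovered. The Background states that the study wants to find the moment when a stable conduction block turns into worsening heart failure, and patients who could benefit from early treatment. The second kind of patient made that turn, yet the written rule allows them into the group that represents stability.

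Two things would be at stake. True cases would be lost from the deteriorated group, and the comparison group would be contaminated. There is also a possible link to the predictor: for inpatients, section 3.7 says the "baseline echocardiogram and BP monitoring will be performed as part of the routine clinical investigations", so a treating team may act on what it shows. If treatment followed abnormal findings, the misclassification would depend on the marker under study.

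**Working it through.** **Step 1. Apply the written rule to four patients.**

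| Course between visits | State at repeat visit | Marker-based class (3.4, 3.11) | Seen elsewhere? |
|---|---|---|---|
| Admitted for heart failure, treated | All markers at baseline values | Non-deteriorated | Yes: event in the logistic regression |
| Worsened, drugs started, not admitted | All markers at baseline values | Non-deteriorated | Yes: drug initiation, secondary outcome |
| Worsened, drugs started | Markers better than at baseline | Improved, hence non-deteriorated | Yes: drug initiation |
| Worsened, drugs started | proBNP still more than 10% up | Deteriorated | Yes |

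The first three rows show the gap. The fourth shows its limit: because the criteria are joined by and/or, one residual criterion keeps the patient in the deteriorated group.

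**Step 2. Reproduce the protocol's sample sizes.** Inputs from section 3.10: strain difference 5, SD 6, two-sided alpha 0.05, share deteriorating p. Power is not stated for this calculation; 80% is assumed.

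Total N = (1.960 + 0.842)² × 6² / (5² × p × (1 − p)) = 11.30 / (p(1 − p)).

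- p = 10%: 11.30 / 0.09 = 125.6; t-test version 128; stated 129.
- p = 20%: 11.30 / 0.16 = 70.6; t-test version 73; stated 73.
- p = 30%: 11.30 / 0.21 = 53.8; t-test version 56; stated 57.
- p = 5%: 11.30 / 0.0475 = 237.9; t-test version 240; stated 220, which does not reproduce.

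The present point does not rest on these figures. The 10% and 20% cases serve as a base for Step 3.

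**Step 3. Illustrate the loss of power.** Let a fraction r of true deteriorators be back at non-deteriorated values. The fraction r is an assumption; no document gives it. Recovered and other deteriorators are assumed to have the same baseline strain.

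- Observed share deteriorating: q(1 − r), with q the true share.
- Contamination of the comparator: c = qr / (1 − q(1 − r)).
- Observed difference: 5(1 − c).
- Comparator variance: 36 + 25c(1 − c).

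Example with q = 10%, r = 20%, N = 129: observed share 8%; c = 0.02 / 0.92 = 0.0217; difference 4.89; group sizes 10.32 and 118.68; standard error √(36/10.32 + 36.53/118.68) = 1.948; 4.89 / 1.948 − 1.96 = 0.55, so power is 71%.

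| True share, N | r = 0 | 10% | 20% | 30% | 50% |
|---|---|---|---|---|---|
| 10%, N = 129 | 81% | 76% | 71% | 65% | 50% |
| 20%, N = 73 | 81% | 76% | 70% | 63% | 47% |

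Most of the loss comes from fewer cases; in the example the difference itself shrinks only from 5 to 4.89. At 10% true deterioration, r = 10% to 50% puts 10 to 50 of every 1000 patients in the wrong group.

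**Step 4. What marker-dependence would do.** Assume true deterioration of 20% with an abnormal and 10% with a normal marker (relative risk 2.0), and recovery fractions r1 and r0. Observed relative risk = 0.20(1 − r1) / [0.10(1 − r0)].

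- r0 = 10%, r1 = 20%: 0.16 / 0.09 = 1.78.
- r0 = 10%, r1 = 30%: 0.14 / 0.09 = 1.56.
- r0 = 10%, r1 = 40%: 0.12 / 0.09 = 1.33.
- r0 = r1 = 20%: 0.16 / 0.08 = 2.0.
- r0 = 20%, r1 = 10%: 0.18 / 0.08 = 2.25.

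So the ratio falls only if full recovery is commoner in marker-abnormal cases. Equal recovery leaves it unchanged but loses a fifth of the cases.

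**The case against.** A reader might infer that the study hides the very cases it looks for. The documents do not support that. An admitted patient is an event in the logistic regression of 3.11, section 3.10 also calls cardiovascular admission a primary outcome variable, and drug initiation is a listed outcome. The pilot in 3.7 counts heart failure in its own right beside ventricular deterioration, so at most the second of these two figures is too low.

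A reader might also infer that the marker's association is biased downwards. That needs recovery to depend on the marker, which is not shown. The markers in the primary hypotheses are strain pattern and myocardial work. Section 3.12 has the echocardiograms analysed in the core lab, from files collected centrally at the latest after the second visit. No section says that treating teams receive strain or work results. A link through ejection fraction or volume is plausible, no more.

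Three further objections deserve weight. First, section 3.11 does not define its comparator as everyone who misses the thresholds, and an admitted patient is not obviously unchanged. That is fair, but the binary outcome in 3.4 gives such a patient no place other than non-deterioration. Second, details of this kind are often left to an analysis plan. Here, however, the protocol itself fixes the classification rule. Third, counting every drug start as deterioration in the main analysis would be a debatable choice of estimand: if treatment followed the baseline echocardiogram, the predictor would be built into the outcome. This objection stands, and it limits the fix to a sensitivity analysis for drug treatment.

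**Conclusion.** The gap is real but bounded. As written, a patient with a heart-failure admission or documented worsening who is fully back to baseline values is classed as non-deteriorated and can enter the comparator of the ANOVA and of any ROC analysis built on the same classification. The logistic regression on admissions and death is not affected.

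The size cannot be derived from the documents. The power losses in Step 3 rest on an assumed recovered fraction and on equal baseline strain. The relative risks in Step 4 rest on assumed risks and recovery fractions, and their direction depends on which marker group recovers more often. Neither set should be read as an estimate for this study. The change is worth making because it is specific and cheap and serves the study's stated aim.

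**What to change.** In 3.4 and 3.11, state that a patient with a heart-failure admission between the two visits is not placed in the unchanged group, and report how many such patients there are.

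Add one sensitivity analysis, reported beside the marker-only classification. In it, a heart-failure admission, or heart-failure drug treatment started for documented worsening after baseline (not because of the baseline echocardiographic findings), counts as deterioration.

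The interval needs one definition, so the one-year and 18-month visit times must be reconciled. This concerns classification only and asks for no change in patient care.

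Cost: wording in two sections and one extra analysis. Admissions, medication and drug initiation are already to be collected (3.1, 3.5). Two burdens remain. The reason for starting treatment must be taken from the record. Section 3.1 also schedules outcome linkage for 3 and 5 years, so an earlier analysis would need interval admissions from the patient record. The sensitivity analysis can inflate the association if treatment in fact followed the baseline echocardiogram, and its report should say so.
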